### 12.6.5 Methods for Handling Dropouts and Missing Data

Missing data will not be imputed, with the exception of missing or partial dates, missing item responses on the CFQ-R, and missing baseline and Visit 4 (week 5) ppFEV1.

Missing or partial dates will be imputed if dates are missing or incomplete for an AE (including death event) or concomitant medication as described in Section 8.0.

Partial dates for the date of CF diagnosis will be imputed. If only 'day' is missing, then impute day with '01'. If 'day' and 'month' are missing, and 'year' is not missing, then impute both month and day with '01'.

Missing item responses will be imputed using the median of item responses within that domain, when no more than half the item responses are missing, for CFQ-R domain scores. See Section 8 for more details.

Missing ppFEV1 data will be imputed only for use in the sensitivity analysis described in section 12.6.1. The FCS multiple imputation method will be used. The multiple imputation will be carried out in SAS using PROC MI. Twenty sets of imputed data will be generated and the default maximum of 100 iterations will be used to attempt to impute values within the appropriate range for each variable, though this may be increased to impute appropriate values.

## 12.6.6 Multiplicity

There will be no multiplicity adjustments for this study.

## 12.6.7 Pooling of Sites

All sites will be pooled together for the analyses.

## 12.7 Pharmacokinetics (PK)

At Visit 2, blood samples for PK testing will be collected pre-dose and at 5±2 minutes and 15±5 minutes after completion of administration of the study drug, for Cohort 1 only.

There will be no additional summary of PK in this SAP. A data transfer from QPS to PRA is not intended. QPS will send a listing of PK results for inclusion in the eTMF

## 12.8 Safety Analyses

The Safety Analysis set will be used to summarize all safety endpoints.

### 12.8.1 Adverse Events

Any condition, event and/or signs and symptoms occurring after signing the informed consent form and before starting study drug treatment should be recorded as medical history in the eCRF. Medical conditions/diseases are considered AEs only if they start or worsen after starting study drug treatment (first application of study drug).

Therefore, an AE includes any condition (including a pre-existing condition) that: 1) was not present prior to study treatment, but appeared or reappeared following initiation of study treatment, or 2) was present prior to study treatment, but worsened during study treatment.

A Treatment Emergent Adverse Event (TEAE) is defined as per Section 8.

Subject incidence of adverse events (AEs) will be summarized by MedDRA system organ class (SOC) and preferred term (PT), severity and relationship to study drug for each treatment group and total. For incidence reporting, subjects will be counted only once within same SOC or PT. All AEs, TEAEs and pertinent subject information will be presented in data listings. Serious adverse events (SAEs), AEs leading to death, and AEs leading to withdrawal from study will be presented in separate listings respectively. An overall summary of AEs will be provided by treatment groups and total.

Missing values for severity will be assigned as 'severe' and missing values for relationship to treatment will be considered as 'related' in the summary.

A summary of AEs by SOC and PT will be tabulated in descending order of frequency by treatment groups and total for the following:

- AEs leading to study discontinuation
- AEs leading to death
- All serious adverse events (SAEs)
- SAEs related to study treatment
- All treatment-emergent AEs (TEAEs)
- Treatment-related TEAEs
- TEAEs by maximum severity. For each system organ class or preferred term, multiple occurrences of events within a subject are counted only once at the highest severity

#### 12.8.1.1 Adverse Events of Special Interest (AESI)

For those adverse events considered as TEAEs of special interest (hyperkalemia/increased potassium) classification will be final before final database lock (DBL).

The total number of AESIs will be summarized for each treatment group and total.

#### 12.8.2 Laboratory Data

All laboratory test results will be reported in International System of Units (SI).

Descriptive summaries of changes from baseline for each laboratory test listed below will be provided for numerical laboratory assessments by visit.

Each laboratory value will be assessed as low, normal or high based on the normal ranges provided by the laboratory. Laboratory shift tables from baseline to each post-baseline visit for lab values evaluation of 'High' 'Low' or 'Normal', when available, will be planned when the baseline results are available.

The categorical lab results will be summarized by frequency and percentage and by visit.

The clinical safety laboratory tests will include the following parameters:

- Hematology: White blood cell count, red blood cell count, red blood cell indices, hemoglobin, hematocrit, platelet count, and a 5-part white blood cell differential (neutrophils, lymphocytes, monocytes, eosinophils, and basophils)
- Clinical chemistry: Liver function tests (ALT, ALP, AST, and gamma glutamyltranspeptidase), electrolytes (sodium, potassium, chloride, and bicarbonate), total bilirubin, blood urea nitrogen, calcium, C-reactive protein, creatinine, glucose, lactate dehydrogenase, total protein, and albumin

- Blood and urine electrolytes: sodium, potassium, chloride, and bicarbonate
- Urinalysis: pH, specific gravity, protein, glucose, and ketones

Pregnancy test results for females of childbearing potential only will be listed by visit for each treatment group.

If multiple assessments per lab test are done on the same date, then the average value will be used. The denominator for the percentages will be the total number of subjects in the treatment group with a baseline and post-baseline value. Laboratory parameters with abnormal clinically significant results will be identified and listed, where available.

### **12.8.3 Vital Signs**

Vital signs (systolic and diastolic blood pressure, heart rate, and body temperature) will be measured at each visit during screening and treatment period.

Observed values and changes from baseline in vital signs will be summarized by vital sign parameter and visit. Descriptive statistics will be shown for baseline, each post-baseline time point, and the change from baseline to each post-baseline time point.

### **12.8.4 Electrocardiograms (ECGs)**

At a minimum, heart rate and the P, PR, QRS, QT, and QTcF intervals will be obtained and entered into the eCRF. The Investigator will also evaluate whether the ECG is normal or abnormal, and if abnormal, whether the abnormality is clinically significant.

The number and percentage of subjects for each category of ECG evaluation will be presented by treatment group and total. ECG shift tables from baseline to visit 5 for clinical interpretation of normal, abnormal, clinically significant abnormal will be presented.

A listing of subjects with ECG assessments, including the clinical evaluation results, will be provided.

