#### *9.6.1.2 Safety Variables*

- Incidence of treatment-emergent AEs
- Changes in vital signs
- Changes in clinical laboratory tests, including urine and blood electrolytes
- Changes in ECGs

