### **11.6    Electrocardiogram**

Computerized 12-lead ECG recordings will be obtained, after the subject has been supine for 5 minutes. Each lead will be recorded for at least 3-5 beats at a speed of 25 mm/sec paper speed and 10 mm/mV amplitude. At a minimum, heart rate and the P, PR, QRS, QT, and QTcF intervals will be obtained and entered into the eCRF. The Investigator will also evaluate whether the ECG is normal or abnormal, and if abnormal, whether the abnormality is clinically significant. A copy of all ECGs will be retained on site and may be collected for central review if required (ie, in case emerging ECG data necessitate expert evaluation).

An ECG may be repeated for quality reasons and additional ECGs may be collected by the Investigator for safety reasons. Any clinically relevant abnormal findings noted at Screening will be exclusionary. Any clinically relevant abnormal findings after the first dose of the study drug will be reported as AEs. Subjects with clinically relevant cardiovascular AEs (or clinically relevant ECG changes) must be withdrawn from the study (see [Section 9.4.4](#)).

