#### **13.6.6 Safety**

Safety data will be summarized for the safety population.

Exposure to the study drug will be summarized. Summaries will include the number of doses received and dose compliance.

All AEs reported after initiation of treatment, and pre-existing conditions that worsen or become more frequent after initiation of treatment will be considered TEAEs. Adverse events will be coded by system order class and preferred term using MedDRA. All recorded AEs will be included in the data listings.

The number and percentage of subjects with TEAEs, SAEs, AEs leading to death, and AEs leading to discontinuation of the study drug will be summarized by preferred term, and where appropriate, system organ class. Deaths, SAEs, and AEs leading to discontinuation of the study drug will also be listed, and narratives will be written.

Summary statistics for actual values and for change from baseline will be tabulated as appropriate for vital signs and clinical laboratory test results. Results of ECGs will be summarized and results of physical examinations will be listed.

All non-study medications received during the treatment period will be considered concomitant medications. Previous and concomitant medications will be coded using the WHO Drug Dictionary and will be summarized.

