### 7.3 Safety Variables

- Incidence of treatment-emergent AEs (TEAEs)
- Changes in vital signs
- Changes in clinical laboratory tests, including urine and blood electrolytes
- Changes in electrocardiograms

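### SAP 12.8.4 specifies only categorical ECG outputs and a listing; it names no summary of the recorded PR, QRS, QT or QTcF values or of their change from baseline

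*SAP*

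**What the plan says.** Both documents name ECG change as a safety variable: "Changes in ECGs" in Protocol 9.6.1.2 and "Changes in electrocardiograms" in SAP 7.3. Protocol 11.6 requires that "heart rate and the P, PR, QRS, QT, and QTcF intervals will be obtained and entered into the eCRF", and SAP 12.8.4 repeats the requirement. The schedules of events place ECGs at screening, Visit 2 (pre-dose) and Visit 5.

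SAP 12.8.4 then specifies three outputs:

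- Counts: "The number and percentage of subjects for each category of ECG evaluation will be presented by treatment group and total".
- Shift table: "ECG shift tables from baseline to visit 5 for clinical interpretation of normal, abnormal, clinically significant abnormal will be presented".
- Listing: "A listing of subjects with ECG assessments, including the clinical evaluation results, will be provided".

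The categories are the investigator's reading of the tracing. Protocol 11.6 makes central review possible but conditional. On analysis, Protocol 13.6.6 says only this of ECGs: "Results of ECGs will be summarized".

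**The concern.** Numeric data are collected for a named safety variable, but the section that governs their analysis turns them into a three-way clinical reading. A programmer who followed 12.8.4 literally would produce no table of interval values by treatment group. If SPX-101 moved PR, QRS or QTcF by a modest, sustained amount in most subjects, most tracings could keep the same category and no specified table would display the shift.

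Cardiac safety is of some interest here. Protocol 7.1 attributes the failure of earlier ENaC inhibitors largely to hyperkalemia. Hyperkalemia is the only pre-defined adverse event of special interest. One of the two Cohort 1 subjects with serious adverse events, both on 120 mg BID, had tachycardia (Protocol 7.3.2), and Cohort 2 uses that dose.

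**Working it through.** **Text comparison.** The documents give no figure for the ECG analysis, so there is nothing to reproduce. The relevant places compare as follows.

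| Place | Numeric change from baseline? |
|---|---|
| SAP 12.8.2, laboratory data | Yes, stated, by visit |
| SAP 12.8.3, vital signs | Yes, stated, by parameter and visit |
| SAP 12.8.4, ECGs | Not stated; categories and a listing |
| Protocol 13.6.6, safety | Stated for vital signs and laboratory tests; ECGs only summarized, form unstated |
| Protocol synopsis, Safety Analysis | General rule: continuous safety variables and their changes are summarized; ECGs are in scope |
| SAP 12.0 | General rule: descriptive statistics for all continuous data; change from baseline not mentioned |
| SAP 4.1, changes from protocol | No ECG departure declared |

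The synopsis rule therefore reaches the ECG intervals, and 12.8.4 neither carries it through nor disclaims it.

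**Illustration of sensitivity.** From the documents: 45 subjects randomized 2:1 in Cohort 2, hence 30 and 15, and the 440 msec entry limit for men. Assumed, because the documents give no QTcF mean or SD: SD of change 10, 15 or 20 msec; mean level 400 to 420 msec with SD 15 or 20 msec; true shift 10 msec. A two-sided 0.05 level is used only to put the two scales on one footing. No ECG test is planned or proposed.

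*Numeric scale.* SE = SD × √(1/15 + 1/30) = 0.316 × SD. The 95% half-width is t(0.975, 43 df) × SE. Approximate power is Φ(10/SE − 1.96).

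| SD (msec) | SE | 95% half-width | Power |
|---|---|---|---|
| 10 | 3.16 | 6.4 | 0.89 |
| 15 | 4.74 | 9.6 | 0.56 |
| 20 | 6.32 | 12.8 | 0.35 |

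*Same shift cut at 440 msec.* The share above the cut is p0 = 1 − Φ((440 − mean)/SD) without the shift and p1 = 1 − Φ((430 − mean)/SD) with it. Extra subjects out of 30 = 30 × (p1 − p0). Power uses the normal approximation for two proportions, with the pooled variance under the null.

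| Mean, SD (msec) | p0 | p1 | Extra of 30 | Power |
|---|---|---|---|---|
| 400, 15 | 0.004 | 0.023 | 0.6 | 0.03 |
| 400, 20 | 0.023 | 0.067 | 1.3 | 0.06 |
| 410, 15 | 0.023 | 0.091 | 2.0 | 0.09 |
| 410, 20 | 0.067 | 0.159 | 2.8 | 0.11 |
| 420, 15 | 0.091 | 0.252 | 4.8 | 0.21 |
| 420, 20 | 0.159 | 0.309 | 4.5 | 0.17 |

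Two limits apply. The 440 msec cut stands in for the investigator's reading, which is not a single threshold. The entry criteria also exclude subjects at or above the limit, so the untruncated normal curve is rough, most of all in the rows with larger p0.

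**The case against.** A reader might infer that the intervals will never be analysed. The documents do not support that. On their wording, the general rules in the protocol synopsis and SAP 12.0 can cover the intervals. Protocol 13.6.6 asks only for a summary, and the table shells, which might settle the matter, are a separate document (SAP Appendix 2).

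A reader might also infer that ECG safety rests solely on site readings, or that categories cannot show a drug effect. Both go too far. A listing is planned, although 12.8.4 does not say whether it prints the intervals. Under Protocol 11.6, clinically relevant findings after the first dose become adverse events, and so reach the adverse event tables. That route depends on the same investigator judgment as the shift table, but it exists. A category table is insensitive to a modest shift, not blind to a large one.

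The two clinical prompts are measured directly elsewhere. Potassium is summarized as change from baseline and by shift table (SAP 12.8.2), and hyperkalemia is tracked as an event of special interest, with none reported in Cohort 1. Heart rate is summarized as a vital sign (SAP 12.8.3), including at 30 minutes and 1, 2 and 4 hours after the first dose. Tachycardia does not by itself point to PR, QRS or QTcF.

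Numeric tables would also have limited reach. The Visit 2 ECG is pre-dose and no study drug is given at Visit 5, so no scheduled ECG follows an in-clinic dose. Protocol 7.2.4 reports measurable plasma drug in Phase 1 only after the single 240 mg dose, only at 5 minutes, and none with repeat dosing up to 120 mg BID.

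All of this stands, and it limits the point to one of specification and sensitivity. It does not remove it. If the general rules apply, 12.8.4 should say so, as the laboratory and vital-sign sections do. If they do not, the synopsis statement is unmet without a declared departure.

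**Conclusion.** The point holds as a minor gap. SAP 12.8.4 specifies no summary of PR, QRS, QT or QTcF values or change, so, followed as written, the named variable has no specified numeric summary. This falls short of the synopsis and of the SAP's own treatment of laboratory data and vital signs.

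Under the assumptions shown, the loss of sensitivity to a 10 msec sustained shift is substantial at every SD tried. The numeric scale is itself only moderate at the larger SDs, and none of these SDs or means comes from the documents. A stronger claim, that the trial could not support its cardiac safety conclusion, is not available: the stated objective is general safety and tolerability, and no separate cardiac conclusion is planned. The primary analysis is unaffected.

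**What to change.** In SAP 12.8.4 add, by treatment group:

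- descriptive statistics of observed values and change from baseline to Visit 5 for PR, QRS, QT and QTcF, on the same visit definition as the shift table;
- counts of subjects at or above pre-specified QTcF cut-points, for example the protocol's own 440 msec for men and 460 msec for women, used for tabulation only.

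Keep the category counts, shift table and listing, and state that the listing prints the interval values. ECG heart rate need not be added, since heart rate is already summarized under vital signs.

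The cost is one or two descriptive tables from data already in the eCRF, with no new procedure and no hypothesis test. The SAP should note that these tables describe sustained effects and cannot show acute post-dose ones.

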### **12.8.5 Physical Examinations and Other Observations Related to Safety**

Physical examination results for all body systems examined will be summarized and listed by visit for each treatment group.

### **12.8.6 Antidrug Antibodies (ADA)**

Anti-Drug Antibody (ADA) response to the study drug will be listed. A summarization of ADA may be considered based on the frequency of ADA detected.

### **12.8.7 Post-Dose FEV1 (Day 1 only)**

A summary of Day 1 change from baseline from pre-dose at each post-dose time point on Day 1 (ie, 30 min, 2 hrs and 4 hours post-dose). Only descriptive statistics will be presented.

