
Cohort 2
 
In Cohort 2, approximately 45 subjects will be randomized in a 2:1 ratio to either SPX-101 120 mg BID or placebo BID. Subjects will be stratified according to concomitant hypertonic saline use, so that approximately 50% will be using hypertonic saline (defined as having used a constant regimen for 28 days prior to screening and planning to continue their usual concentration without change for 28 days post-randomization). The decision to use 120 mg BID in Cohort 2 was based on the relatively greater improvements in the lung function at that dose in Cohort 1, and a need to define the variability in response within the population.
 
For each cohort, there will be 5 clinic visits and 2 telephone calls: Visit 1 (Screening; Day -28 to Day -3); Visit 2 (Randomization; Day 1); Visit 3 (Day 8 -1); Visit 4 (Day 15 -2/+1); telephone
	

call (Day 22 ± 3); Visit 5 (Day 29 ± 2; end-of-treatment); and a follow-up telephone call 2 days later (Day 31 ± 1; end-of-study). All study visits for an individual subject will be scheduled at approximately the same time of day to minimize the confounding effects of diurnal variation in lung function, background therapies, and daily chest physiotherapy regimens. Subjects will be screened at Visit 1 and then will enter a variable-length screening period of 3 to 28 days, to time the randomization so that the first dose of the investigational product will coincide, if applicable, to the first day of an inhaled antibiotic cycle. In Cohort 1, subjects who still met the randomization criteria on Day 1 (Visit 2) were randomized to 1 of the 3 treatment groups. In Cohort 2 subjects who still meet the randomization criteria on Day 1 (Visit 2) will be randomized either to the treatment or placebo group, as described.

At Visits 2, 3, and 4, after completing spirometry and other assessments, subjects will self-administer the study medication in the clinic. On Day 1 (Visit 2) only, subjects will be monitored for safety for the first 4 hours after completion of administration of the study drug. Monitoring will include spirometry, vital signs, and adverse event (AE) assessments as described in more detail in the protocol. After the 4-hour postdose assessments are complete, subjects who have tolerated the study medication will be discharged with a sufficient supply of medication to take BID on an outpatient basis until their next clinic visit.

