### 7.3.2 Rationale for Cohort 2 Dosage

In Cohort 1, a total of 45 adult subjects with cystic fibrosis were treated with one of two doses of SPX-101 (60 mg BID and 120 mg BID) or matching placebo, and 40 subjects completed the study.

The SPX-101 120 mg BID group demonstrated an improvement in the primary endpoint, trough ppFEV1 at day 28, (least squares mean difference from placebo  $\pm$  standard error) of  $3.08 \pm 2.411$ ;  $p = 0.21$  for the SPX-101 60 mg BID group and  $5.19 \pm 2.606$ ;  $p = 0.05$  for the SPX-101 120 mg BID group (source: Table 14.2.1.1).

SPX-101 was well tolerated in both dose groups with no dose-limiting toxicity observed. There were no deaths in the study. Two subjects had serious adverse events (SAEs); one subject had tachycardia and one subject had cough and dyspnea, and both subjects were in the SPX-101 120 mg BID group. Treatment-emergent adverse events (TEAEs) were reported for 71.4%, 66.7%, and 75.0% of subjects in the placebo, SPX-101 60 mg BID, and SPX-101 120 mg BID treatment groups, respectively. TEAEs that coded to the Medical Dictionary for Regulatory Activities (MedDRA) System Organ Class of Respiratory, Thoracic, and

Mediastinal Disorders were reported for 35.7%, 53.3%, and 43.8% of subjects in the placebo, SPX-101 60 mg BID, and SPX-101 120 mg BID treatment groups, respectively. Although more respiratory TEAEs were reported for subjects on active treatment than placebo, the most commonly reported respiratory TEAEs were associated with the therapeutic effect of SPX-101: sputum increased was reported for 7.1%, 20%, and 12.5% of subjects in the placebo, SPX-101 60 mg BID, and SPX-101 120 mg BID treatment groups, respectively; and cough was reported for 0%, 26.7%, and 6.3% of subjects in the placebo, SPX-101 60 mg BID and SPX-101 120 mg BID treatment groups, respectively. The only pre-defined adverse event of special interest was hyperkalemia, which was not reported for subjects in any treatment group. [Table 1](#) shows these results.

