#### **10.2.2 Randomization and Study Procedures**

- Randomization using IXRS

- The Investigator or designee will issue the eTrack study nebulizer and will train subjects on its use and all study procedures, and will review all instructional materials and ensure subjects understand all procedures and instructions
- Study medication administration and postdose monitoring for at least 4 hours after completion of administration
  - Blood for PK analysis will be collected at  $5 \pm 2$  minutes and  $15 \pm 3$  minutes after completion of administration of the study drug (Cohort 1 only)
  - Post-dose spirometry at  $30 (\pm 15)$  minutes, 2 hours ( $\pm 15$  minutes), and 4 hours ( $\pm 15$  minutes) after completion of administration of the study drug
  - Vital signs at  $30 (\pm 15)$  minutes, 1 hour ( $\pm 15$  minutes), 2 hours ( $\pm 15$  minutes), and 4 hours ( $\pm 15$  minutes) after completion of administration of the study drug
- Dispense study medication, nebulizer, and baby bottle sterilizer
- Schedule the subject's next visit and review instructions (See Appendix 4, [Section 18.4](#))

If the subject experiences symptoms of acute bronchospasm following the first dose of study medication, the subject should be treated with SABAs or other treatment at the discretion of the Investigator and continued to be observed for at least 2 hours post-SABA or the 4-hour postdose timepoint, whichever is longer. If the subject's bronchospasm has been relieved and the subject is stable for at least 30 minutes at the 2-hour post-SABA or 4-hour postdose timepoint, the subject may continue in the trial at the discretion of the Investigator. If medically essential, the Investigator may elect to require that the subject be pre-treated with a SABA or other medication before every subsequent dose, or the PI may withdraw the subject from the study. If the subject requires pre-treatment with a SABA or other medication for subsequent doses, this drug will be recorded as a concomitant medication, and the bronchospasm will be reported as an AE. Additional follow-up procedures may be instituted at the discretion of the Investigator.

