### 11.3 Pulmonary Function Tests

Spirometry will be performed at all clinic visits using equipment provided by the centralized spirometry vendor, Biomedical Systems (BMS). Spirometry will be performed in accordance with ATS/ERS guidelines and the GLI predictors of spirometric lung volume normal ranges [2; 3]. At Visit 2, spirometry will be performed pre-dose, and postdose at 30 minutes, 2 hours, and 4 hours postdose after completion of administration of the study drug. At all other visits, only pre-dose spirometry will be performed. The following parameters will be recorded:

- Absolute FEV1 and ppFEV1
- Absolute FVC and ppFVC

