### 12.2 Serious Adverse Events

An SAE is any untoward medical occurrence or effect that meets any of the following criteria:

- results in death;
- is life-threatening (refers to events during which a subject was actually at risk of death, and not to events that might have become life-threatening if they had occurred in a more severe form or if the subject had not received treatment);
- requires inpatient hospitalization (> 24 hours) or causes prolongation of existing inpatient hospitalization;
- results in a persistent or significant disability or incapacity;
- is a congenital abnormality/birth defect in the offspring of a study subject;
- is an important medical event that does not meet any of the above criteria but may require medical intervention to prevent one of the outcomes listed above, or is considered medically important by the Investigator; examples of important medical events include:
  - Bronchospasm requiring treatment in the emergency department or at home
  - Development of a blood dyscrasia
  - Diagnosis of a substance use disorder

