## 12.0 Statistical Methods

All statistical programming will use SAS® version 9.4 or higher.

All statistical analyses will be performed using a two-sided alpha = 0.05, unless otherwise specified.

For two sequential cohorts, each cohort will be analyzed separately based on its own baseline.

Unless otherwise specified, descriptive summaries will be tabulated by treatment groups and overall. Categorical data will be presented using counts and percentages, with the number of subjects in each category as the denominator for percentages. Percentages will be rounded to one decimal place except 100% will be displayed without any decimal places and percentages will not be displayed for zero counts.

All continuous data will be summarized using the number of observations (n), mean, standard deviation (SD), median, first quartile, third quartile, minimum, and maximum. Minimum and maximum will be rounded to the precision of the original value. Mean and median will be

Sponsor: SPYRYX Biosciences

Protocol no: SPX-101-CF-201

---

rounded to one decimal place greater than the precision of the original value. The SD will be rounded to two decimal places greater than the precision of the original value.

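### The Day 1 post-dose FEV1 summary shows the worst value at each time but not how many subjects had an acute fall, and it has no rule for readings after rescue

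*SAP*

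**What the plan says.** Protocol 11.3 sets the Day 1 measurements: "spirometry will be performed pre-dose, and postdose at 30 minutes, 2 hours, and 4 hours postdose after completion of administration of the study drug". Protocol 10.2.2 gives each post-dose test a window of 15 minutes either side.

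SAP 12.8.7 plans a summary of change from pre-dose at each of these times and limits it: "ie, 30 min, 2 hrs and 4 hours post-dose). Only descriptive statistics will be presented". It does not say whether the change is absolute or percent. SAP 12.0 defines the content: "All continuous data will be summarized using the number of observations (n), mean, standard deviation (SD), median, first quartile, third quartile, minimum, and maximum".

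For acute bronchospasm after the first dose, Protocol 10.2.2 says "the subject should be treated with SABAs or other treatment at the discretion of the Investigator". The same section keeps the subject under observation through the 4 h time point or longer, so rescue can precede the 2 h and 4 h tests. Neither document says how spirometry after rescue is handled. SAP 8.0 (Change from Baseline) calculates a change for every subject with a baseline and a post-baseline value and excludes only missing changes.

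SAP 12.6.4 does tabulate ppFEV1 change in categories, including falls of 10 or more, but by visit. In the visit-window table of SAP 8.0, Day 1 is the baseline visit, so the Day 1 post-dose readings have no such table.

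**The concern.** Acute airway narrowing after an inhaled drug may affect only a few subjects. The useful safety result is then how many subjects fell and by how much, by arm. Time-point descriptives answer a different question: how the arm as a whole moved.

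Post-dose spirometry is the only objective airway measurement scheduled after the first dose. Protocol Table 3 otherwise schedules vital signs (blood pressure, heart rate, temperature) and AE questioning at the post-dose times; the physical examination is pre-dose. If these readings are not turned into a per-subject result, a reader of the Cohort 2 report cannot compare the frequency of first-dose falls on 120 mg and on placebo.

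There is reason to want that comparison. Protocol 7.3.2 reports respiratory treatment-emergent AEs in 35.7%, 53.3% and 43.8% of the placebo, 60 mg and 120 mg groups in Cohort 1, and treats the commonest of them, increased sputum and cough, as linked to the therapeutic effect. Per-subject Day 1 spirometry would bear directly on acute narrowing.

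**Working it through.** The documents give no figure for Day 1 tolerability, so there is nothing to reproduce. The check has two parts.

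**1. What the planned statistics can show**

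Inputs:
- Cohort 2 has 45 subjects at 2:1 (SAP 6.1), so n = 30 on 120 mg and 15 on placebo.
- Assumed, because the documents give no rate or size of acute fall: k subjects fall by d percent at 30 min and all others stay at 0.

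Formula: mean = k × d / n.

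| n | k | d | Mean | Lower quartile | Minimum |
|---|---|---|---|---|---|
| 30 | 1 | -20 | -0.67 | 0 | -20 |
| 30 | 2 | -20 | -1.33 | 0 | -20 |
| 30 | 3 | -20 | -2.00 | 0 | -20 |

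For d from -15 to -30 and k from 1 to 3, the mean runs from 1 × (-15)/30 = -0.50 to 3 × (-30)/30 = -3.00, and the lower quartile stays at 0.

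The minimum reveals that a fall occurred but is the same for one subject or three. The SD does move. For k = 3 it is √[(3 × 18² + 27 × 2²)/29] = √(1080/29) = 6.1; for k = 1 it is √[(19.33² + 29 × 0.67²)/29] ≈ 3.7. In real data, ordinary test-to-test variation also feeds the SD, so the count cannot be read back from it. Nor do the mean and minimum identify the count: one subject at -20 and 29 at -40/29 = -1.38 also give a mean of (-20 - 40)/30 = -2.00 and a minimum of -20.

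*Rescue.* Assume the three subjects receive a SABA after the 30 min test and are back to 0 by 2 h. The 30 min row has mean -2.00 and minimum -20; the 2 h row has mean 0 and minimum 0. If rescue comes before the 30 min test, which can be as late as 45 min, that minimum can be masked too. Dropping post-rescue readings does not repair the later rows: the 27 remaining subjects still give mean 0 and minimum 0, now without the worst-affected subjects.

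**2. Which planned output counts which subject**

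| Subject on Day 1 | SAP 12.8.7 | AE tables, SAP 12.8.1 |
|---|---|---|
| Symptoms, rescued | Later rows carry post-rescue values by default | Counted once per term |
| Symptoms, not rescued | Visible individually only if worst in the arm at that time | Counted once per term |
| Fall without symptoms | Visible individually only if worst in the arm at that time | No rule requires an AE |

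The last cell follows from comparing the AE rules. Day 1 AE assessment asks about symptoms (Protocol Table 3, footnote b). The protocol says when abnormal vital signs (11.4), ECGs (11.6, 12.4.2), laboratory results (12.4.1) and physical findings (12.4.2) become AEs. It has no matching rule for spirometry. The general definition in 12.1 is wide enough for an investigator to report a fall, but that is a matter of judgement.

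**The case against.** The strongest reply is that first-dose tolerability is already well covered. Rescue under Protocol 10.2.2 is prompted by symptoms, so a rescued subject is under observation and reportable. AEs are assessed at 30 min and 1, 2 and 4 h (Protocol 11.7). For subjects who then need pre-treatment, the protocol states that "this drug will be recorded as a concomitant medication, and the bronchospasm will be reported as an AE". One listed example of a serious event is "Bronchospasm requiring treatment in the emergency department or at home". SAP 12.8.1 counts subjects by preferred term, severity and relationship. An independent safety board also sees unblinded data, including at the Cohort 2 midpoint. Subjects with falls but no symptoms are not rescued under 10.2.2, so their later readings are not masked. All of this stands and narrows the point to the count of objective falls.

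Several stronger readings are tempting, and the documents do not support them:
- *A reader might infer that only a mean is reported.* SAP 12.0 includes quartiles, minimum and maximum.
- *That the SAP states that post-rescue values are kept.* It is silent; inclusion follows from the default rule in SAP 8.0. The table shells are a separate document, so a flag or listing there cannot be ruled out.
- *That the 120 mg choice rests on tolerability.* The Synopsis bases it on greater lung-function improvement and a need to define variability; 7.3.2 cites the absence of dose-limiting safety concerns only as support.
- *That Cohort 1 already showed acute narrowing at 120 mg.* On serious events, 7.3.2 says "one subject had tachycardia and one subject had cough and dyspnea, and both subjects were in the SPX-101 120 mg BID group". It gives no day, relation to dosing or bronchospasm, and cough was less frequent at 120 mg (6.3%) than at 60 mg (26.7%).

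**Conclusion.** The point holds in a limited form. No output in the SAP counts subjects with an acute Day 1 fall in FEV1 or gives a per-subject lowest value, and post-rescue readings enter the 2 h and 4 h rows by default. What is missing is the frequency of objective falls, including any without symptoms; symptomatic bronchospasm is not lost.

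The illustrated size, a mean of -0.67% to -2.00% with an unchanged minimum for 1 to 3 of 30 subjects falling 20%, rests wholly on assumed falls with everyone else unchanged. It shows what the statistics can distinguish, not what is likely to happen. The conclusion also depends on the table shells not already providing a count, which cannot be checked.

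This concerns one descriptive safety table. It does not touch the primary analysis, the power or any decision rule, but it is worth correcting because the spirometry is already collected.

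**What to change.** In SAP 12.8.7, before Cohort 2 database lock, add by arm:

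- **(a) Per-subject falls.** Each subject's lowest Day 1 post-dose FEV1 as percent change from pre-dose, with the number and percentage at or beyond reporting thresholds that the sponsor prespecifies. The 10% in the exacerbation criteria and the 15% in the FEV1 stability criterion serve other purposes, so the sponsor should justify its own values.
- **(b) Rescue.** The number and percentage who received rescue on Day 1. Flag these subjects in the listing and keep them in the count under (a). Where the time of rescue is available, show the time-point summaries with and without their post-rescue values, rather than simply dropping them.

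The cost is one extra descriptive table. Rescue timing needs confirming in the eCRF or source, because Protocol 9.5.7 asks for dates of administration and does not mention clock time. If times are missing, the lowest values, the counts and the rescue flag can still be produced; only the split summaries cannot.

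These are reporting thresholds only. No treatment or stopping rule is proposed.
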